Participants will remain on the experimental diets for the indicated time periods, or until they develop organ dysfunction associated with Cho deficiency (liver damage = >1.5-fold increase in aspartate aminotransferase (AST) or muscle damage = >5-fold increase in creatine kinase (CK)). A clinical chemistry panel will be run at the beginning of the study (Screening) and at the beginning and end of each dietary period of the study (see Figure 1, appendix). If they develop organ dysfunction at the end of any of the experimental diet periods, subjects will follow the abnormal lab values protocol (Appendix Figure 6). We have extensive experience with these diet formulations (24, 52, 55) and have not observed clinically significant liver or muscle damage in individuals fed the 10% Cho diet for 2 weeks or less. After longer periods, clinical liver and muscle damage was noted, and reversed with 2 weeks of feeding 100% Cho diet. No other toxicity was observed after as long as 7 weeks on the 10% Cho diet (24, 52, 55). A urine pregnancy test will be performed on pre-menopausal women at the beginning and end of each dietary arm.

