1.2 Name and Description of Investigational Product or Intervention

Diets: The experimental diets, delivering 100%, 50% and 25% of the recommended intake of Cho (in all forms) (550 mg Cho/70 kg body weight/d), are identical except for the bread that we offer (Cho in the bread will be varied to deliver the desired Cho above that delivered by the base 25% Cho diet as described previously (1)). The base 10% Cho diet is composed of 0.8 g high biologic value protein/kg [current Recommended Dietary

Allowance (RDA)], with 30% kcal coming from fat and the remaining kcal from carbohydrate; diets are purchased commercial meals that have been measured for total nutritional values to acquire specific choline amounts for controlled choline intake. These diets were designed to bracket the range of dietary intake observed in several large published human population studies (18-23, 75). We have experience preparing and using diets with similar choline controls for more than 60 days per subject in our previously published studies (10, 24, 25, 51, 55).

Total food intake will be adjusted to be isocaloric (using snacks that contain minimal choline in any form) and to provide adequate intakes of macro- and micronutrients. All diets meet or exceed the Estimated Average Requirement for methionine plus cysteine, and the RDI for vitamins B₁₂, B₆, and folate. A multivitamin supplement (Kirkland Signature Daily Multi Vitamins and Minerals; Costco, Seattle, WA) provides vitamins and minerals at or above the RDI or Adequate Intake. Subjects will also be given a dietary supplement containing the RDI of magnesium and 1.5 times the Adequate Intake of calcium (Calcium Magnesium Complex; Vitamin Shoppe, North Bergen, NJ). We will use a 3-day diet menu of equivalent diets to allow for meal diversity. On the last 5 days of a diet period, subjects will consume 22% of their total Cho in the form of Cho chloride-(trimethyl-d9; 98%; Cambridge Isotope Laboratories, Tewksbury, MA, USA) replacing non-labeled Cho mole for mole in the bread. We will confirm total Cho content of diets by LC-MS/MS analysis of samples of duplicate food portions as previously described (1). Cho content and stability during storage of Cho in the bread will be separately determined.

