On the last 5 days of a diet period, subjects will consume 22% of their total dietary Cho in the form of Cho chloride-(trimethyl-d9; 98%; Cambridge Isotope Laboratories, Tewksbury, MA, USA). This proportion was shown by others to result in adequate enrichment of isotopic Cho in adults (89). This Cho will be diluted in the plasma pool of Cho and then in the liver and total body tissue pool of Cho, and metabolites will be formed (**Figure 5, appendix**). We will collect a plasma sample before (baseline) and after (post dosing) each 5-day feeding of deuterated Cho.

Cho is stored in the body primarily as Cho, phosphoCho, glycerophosphoCho, PtdCho and sphingomyelin. Acetylcholine and CDP-Cho constitute a very small portion of the Cho pool and will not be measured. In plasma, phosphoCho is hydrolyzed to Cho by alkaline phosphatase; thus, measuring enrichment of Cho includes a measure of phosphoCho. New Cho enters the pool from the diet and from *de novo* synthesis catalyzed by PEMT. The sum of the metabolite enrichments of Cho-d9, glycerophosphoCho-d9, sphingomyelin-d9 and PtdCho-d9 will be calculated relative to the sum of Cho compounds with no d9. The presence of Cho d3 compounds will be a measure of recycling of a methyl group into Cho via the PEMT pathway, and will be considered to be part of the unenriched Cho pool. Betaine d3 will not be considered part of the Cho pool, but its formation will allow us to adjust our assumptions as to how much of administered label is lost from the Cho pool compartment. We expect that betaine formation will be significant.

Isotope enrichments in each of the Cho-containing compounds will be measured using LC-MS/MSAs described above (89). We will calculate enrichment for each Cho-containing molecule as well as for the combination of the Cho molecules (total); we expect that total Cho enrichment will be what is used in our analyses, but examination of the enrichment of the individual Cho-containing species may allow us to refine our mathematical

compartment models for Cho distribution at 5 days.

Estimated total body Cho pool size is calculated using the following mass balance equations:

$$1. \quad (F_a \times a) + (F_b \times b) = (F_c \times c)$$

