Where F_a is the isotope abundance of deuterium in the isotopic dose; a is the amount of the absorbed isotopic dose (absorption assumed to be 100%); F_b is the isotope abundance of deuterium in the endogenous Cho pool (measured at baseline before 5-day deuterium treatment); b is the amount of the endogenous Cho pool at baseline; F_c is the isotope abundance of deuterium in the total Cho pool ($F = {}^2\text{H}/[{}^1\text{H} + {}^2\text{H}]$) after 5-day dosing; c is the amount of the total Cho pool after dosing.

F_a , F_b and F_c are measured by isotope ratio mass spectrometry.

a is calculated from administered dose

$$2. \quad c = a + b$$

$$3. \quad b = \text{body pool at baseline (unknown)} = a \frac{(F_a - F_c)}{F_c - F_b}$$

Though we will call the estimate derived from the above a measure of total body pool size, it is really just an estimate of the size of the pool that dietary Cho equilibrates with by 5 days (likely smaller than the total body pool). We must make a number of assumptions, discussed below, to arrive at such an estimate. Each assumption certainly affects our estimations of pool size, and as we collect data we will have to model outcomes if we alter these assumptions.

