The use of isotope dilution to estimate Cho pools size has not been used before, but as noted above is an approach that has been proved successful for total body water (90) and Vitamin A (12). For both of these methods, a single bolus of isotopic label can be used. For both of these it is important that the isotopic label equilibrates rapidly with the body pool. We know that Cho equilibrates within minutes with the vascular and liver pools of Cho, but that equilibration with the PtdCho-bound Cho takes hours to days. For this reason, we propose to administer deuterated Cho for 5 days. We realize that our diet depletion protocol will result in a decline in body pool size during these 5 days, but suggest that the decline during the previous 11 days will be larger and make the resulting error in pool size estimation acceptable. Caudill used 3 weeks as her equilibration period (89), but such a long period would provide an estimate of average Cho pool size during the diet intervention rather than at the end of the intervention. Based on our best estimates of Cho turnover in the free and esterified pools, we believe that a 5-day isotope equilibration will work best for the purposes of the study. The equation for calculating Vitamin A total body pool also includes a correction factor for efficiency of absorption of Vitamin A (12). For Cho, we are assuming that efficiency of absorption is 100% (studies described below in SubAlm 1a will help us to test/revise this assumption). This likely is an overestimate, but will result in an overestimation of pool size that will be a constant error for all diet periods, thereby the calculation of the change in pool size caused by a diet period should not be appreciably altered. Similarly, the assumption that little Cho is lost to renal excretion is not true, as the metabolites betaine and TMA are excreted in the urine. Such losses of label in urine will result in an underestimate of Cho pool sizes, but this underestimation of pool size will be a constant error for all diet periods, and changes in pool size should not be affected. We also assume

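### Section 5.1 defines choline pool size for a 5-day labelled feed, but the visits give one day-12 bolus; its urinary-loss direction and constant-error argument are also wrong as written

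*Combined protocol and SAP*

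**What the plan says.** Pool size is the response that the score is built to predict (Section 6.3) and the yardstick of the primary objective (Section 2.1). Two labelling schedules stand in the current text.

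- **Five-day feed.** Section 5.1: "On the last 5 days of a diet period, subjects will consume 22% of their total dietary Cho in the form of Cho" chloride. Section 1.2 agrees: "subjects will consume 22% of their total Cho in the form of Cho". Sampling follows the feed: "We will collect a plasma sample before (baseline) and after (post dosing) each 5-day feeding of deuterated Cho". So do the equation terms: Fb is "measured at baseline before 5-day deuterium treatment", and Fc is taken after the 5 days. The text adds that "b is the amount of the endogenous Cho pool at baseline" and that "a is calculated from administered dose". The reason for 5 days is that "equilibration with the PtdCho-bound Cho takes hours to days"; then, "For this reason, we propose to administer deuterated Cho for 5 days".
- **Single bolus.** The Synopsis and Sections 3.1 and 7 give 250 mg of d9-choline on day 12. Section 4.2 (Visit 4) gives a bolus in a beverage after the 0-hour draw, without repeating the amount. Later blood is drawn at 6 hours and, fasting, on days 13, 14 and 15. The Synopsis names a pre-bolus baseline and an end-of-period sample for pool size. Section 7 says the label replaces unlabelled bread choline on a molar basis.

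Section 5.1 then argues that incomplete absorption and urinary loss of label produce errors that are the same in every diet period, and that PEMT synthesis matters little. It concludes that differences between diets are safe. It states that urinary loss makes the pool look too small.

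**The concern.** The score is trained and judged against this one derived quantity, pooled over three diets. If its terms describe a schedule that is not used, an analyst must decide which sample supplies Fc, which day's pool is being estimated, and whether three days is long enough for the slow phospholipid pool. The protocol answers these questions only for the feed.

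The constant-error argument also matters because it is the plan's reason for not correcting the estimate. An error that rises with intake would make pools look larger on the 100% diet whatever the true stores, and could favour biomarkers of recent intake over biomarkers of stores. That distinction is what the score is meant to make.

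**Working it through.** **Inputs.** Intakes are 550, 275 and 137.5 mg/d at 70 kg (Synopsis). The base diet is 25% (Synopsis) or 10% (Section 1.2). The bolus is 250 mg. The interval from bolus to the day-15 sample is 3 days. The documents give neither pool size nor turnover. Molar masses of 104.17 (choline) and 113.23 (d9-choline) g/mol are assumed.

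**1. Equation 3.** Solving Equations 1 and 2 for b gives b = a(Fa − Fc)/(Fc − Fb), as printed. With a = 250 mg and a true pool of 20,000 mg it returns 20,000 mg. The algebra is sound and suits a single dose.

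**2. Bread replacement on the 25% diet.** Molar equivalent of the bolus: 250 / 113.23 × 104.17 = 230 mg. Choline in bread: 137.5 − 137.5 = 0 mg (25% base) or 137.5 − 55 = 82.5 mg (10% base). Shortfall: 230 or 147.5 mg. Mean intake over days 12 to 14 is then 137.5 + 230/3 = 214 or 137.5 + 147.5/3 = 187 mg/d, against 137.5 planned.

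**3. Label loss before mixing.** If a fraction f of the label is retained, Fc = (Fa·f·a + Fb·b)/(f·a + b). Then (Fa − Fc)/(Fc − Fb) = b/(f·a), and Equation 3 returns b/f.

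| Lost (assumed) | f | Returned pool |
|---|---|---|
| 10% | 0.9 | 1.11 b |
| 20% | 0.8 | 1.25 b |
| 30% | 0.7 | 1.43 b |

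The error is upward and multiplicative. True pools of 20,000 and 16,000 mg (assumed) with f = 0.8 return 25,000 and 20,000 mg. The change becomes 5,000 instead of 4,000 mg, while the ratio stays at 0.8.

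**4. Target: the pre-dose pool b.** Assume one mixed pool, full absorption, no losses, and a bolus added to the diet. Equation 3 then returns b + 3 × intake, so the excess is 412.5, 825 and 1,650 mg on the 25%, 50% and 100% diets. The 100% v 25% difference is 1,237.5 mg with no true difference in pools. If the bolus replaced 230 mg of bread choline on the 100% diet, 1,650 would fall to 1,420 mg, still 3.4 times 412.5. The 5-day feed behaves similarly: 5 × intake less 5 × 0.22 × intake is 3.9 × intake, or 536, 1,073 and 2,145 mg. The bolus is therefore not the cause.

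**5. Target: the end-of-period pool.** With fractional turnover k per day, label falls to a·exp(−3k), and Equation 3 returns the end-of-period unlabelled pool × exp(3k).

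- *Same k on all diets:* a common multiplier. For a 10 g pool and k = 550/10,000, it is exp(0.165) = 1.179.
- *Losses equal to intake (k = intake/b):* the pool is stable and Equation 3 returns b × exp(3 × intake/b). For equal true pools, the 100% v 25% ratio is exp(3 × 412.5/b).

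| Assumed pool | Apparent ratio (truth 1.00) |
|---|---|
| 5 g | 1.28 |
| 20 g | 1.06 |
| 50 g | 1.03 |

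**The case against.** The best defence is that only wording is stale. Equations 1 to 3 are a generic dose, pre-dose and post-dose balance; the dose term is whatever was administered; and the Synopsis names a pre-bolus and an end-of-period sample. This stands as far as the formula goes. It does not supply a named Fc sample in Section 4.2, a target day, or a reason for about 72 hours.

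A reader might infer that the schedule conflict itself distorts pool size fourfold, since the feed would deliver 605 mg of label on the 100% diet and 151 mg on the 25% diet. The documents do not support this: it requires entering a dose that nobody received, contrary to the definition of a.

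A reader might also infer that the error must differ by diet whatever is being estimated. That is too strong. Section 5.1 shows interest in the pool at the end of the intervention, and against that target equal fractional turnover and retention give a common multiplier. The stable-pool case above also fits poorly with the decline the protocol expects on depletion diets. A multiplier equal in all diets and subjects leaves the correlation, which is the primary objective, unchanged.

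The protocol is partly candid. It says the estimate is only the pool reached by 5 days, promises to model other assumptions, plans to use betaine formation to adjust for label loss, and under SubAim 1a measures label in 24-hour urine and compares pool size with liver spectroscopy. These steps test assumptions; none is a rule for correcting the estimate.

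On bread replacement, the beverage in Visit 4 suggests leftover wording. The bolus would still add choline on the 25% diet, and its effect on day-15 biomarkers cannot be sized from the documents.

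**Conclusion.** The point holds, and the text should be fixed before analysis. Three parts need only the documents and algebra: two incompatible labelling schedules are in force; the urinary-loss direction is reversed; and a loss multiplier scales absolute between-diet changes, which Section 5.1 says are untouched. The molar replacement in Section 7 also cannot be met on the 25% diet, given the assumed molar masses.

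The diet-dependent part is conditional. Against the pre-dose pool that Equation 3 defines, omitted unlabelled intake differs fourfold between the 100% and 25% diets when the bolus is added to the diet. Against the end-of-period pool, the error depends on diet only if fractional turnover or label retention does. On the ratio scale it could be appreciable (1.28 at 5 g) or slight (1.03 at 50 g), under a one-pool model with losses equal to intake. The documents do not show that the score's correlation with pool size will be biased; they show that the argument ruling this out does not work.

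**What to change.** 1. Rewrite Sections 1.2 and 5.1 for the bolus: a = 250 mg d9-choline, Fb = day-12 pre-dose, Fc = a named post-dose sample. State whether the target is the day-12 or the end-of-period pool, and replace the 5-day rationale with one for the time used.
2. Correct the direction of the urinary-loss error and delete the constant-error statements. Correct a for the label measured in the 24-hour urine collections in each diet period.
3. Use enrichment in the fasting samples of days 13, 14 and 15 to look for a plateau or a log-linear decline. Section 4.2 names the d9 assay only for days 12 and 15, so specify it for days 13 and 14. Apply a turnover correction or back-extrapolation only if mixing looks complete; otherwise report it as a sensitivity analysis. In either case, check that the score holds under it.
4. State one base diet, and say that the bolus is additional wherever bread choline cannot be replaced.
5. Keep day-15 biomarkers primary, and add a sensitivity analysis with the day-12 pre-bolus metabolomics sample.

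The cost is protocol and SAP wording, some modelling, and possibly extra d9 assays on blood already drawn. No visit or draw is added. A slope from three points is imprecise, slow phospholipid mixing may bend it, and any correction adds variance to the pool estimate.

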that *de novo* formation of PtdCho by phosphatidylethanolamine N-methyltransferase (PEMT) during the 5 days of isotope administration is small compared to body pool size; in women with estrogen this dilution of isotopic label would be greater than in men and postmenopausal women. We believe that the contribution of PEMT will not appreciably change the estimates of pool size that we obtain. To reiterate, as long as the assumptions are uniform in the equation used across diet periods, treatment effects should not be affected.

We propose to use deuterium labeling rather than ^{13}C . The natural abundance of deuterium is $\sim 0.015\%$ compared to hydrogen at $>99.9\%$, whereas those of ^{13}C and ^{12}C are 1.1% and 98.9% , respectively. This makes it easier to attain satisfactory enrichment with lower doses of deuterium. However, deuterium can shift within or between molecules through proton exchange, but this usually occurs under harsh conditions (12). The Caudill data using deuterated Cho suggests that proton exchange is not a significant problem in human studies (89). Using d9-Cho relative to 1,1,2,2-d4-Cho allows us to better differentiate by mass (9 vs 4 mass units). Deuterium labeled Cho is also 6x less expensive than ^{13}C -Cho.

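### Section 5.1 gives urinary label loss the wrong sign: with a fixed at the dose given, loss makes the choline pool estimate too large, and changes in pool size are not protected

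*Combined protocol and SAP*

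**What the plan says.** Section 5.1 estimates the body choline pool as b = a(Fa − Fc)/(Fc − Fb) (Eq. 3). Absorption is taken as complete, and "a is calculated from administered dose"; there is no term for label that leaves the pool. The text says that assuming full absorption "will result in an overestimation of pool size that will be a constant error for all diet periods". For urinary loss it states the opposite direction, "Such losses of label in urine will result in an underestimate of Cho pool sizes", and adds that "this underestimation of pool size will be a constant error for all diet periods, and changes in pool size should not be affected". It concludes that "as long as the assumptions are uniform in the equation used across diet periods, treatment effects should not be affected".

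The target is described in two ways. In the list of equation terms, "b is the amount of the endogenous Cho pool at baseline". Yet a three-week labelling period is rejected because it "would provide an estimate of average Cho pool size during the diet intervention rather than at the end of the intervention", so the pool wanted is the one at the end.

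The loss is to be measured. SubAim 1a (Sections 2.2 and 6.1) and the year-1 validation in Section 5.1 plan urine assays, and Section 4.2 schedules 24-hour urines from day 12 in each arm. Section 5.1 also expects to revise its loss assumption from betaine formation and to model altered assumptions. No section writes the loss into Eq. 3.

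**The concern.** Unabsorbed label and label lost in urine are the same kind of error: less label is in the pool than a assumes. They cannot bias Eq. 3 in opposite directions. The argument that the error cancels between diets also treats it as an added constant, whereas it multiplies the pool. Using one equation on every diet does not make the fractional loss equal on every diet or in every person.

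Pool size by isotope dilution is the reference measure for Aim 1, with a target above 90% prediction accuracy (Synopsis). It is also the response in the pooled OPLS-R model and a response for SubAim 1c (Section 6.3). Loss that varies between people or diets goes straight into that response.

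**Working it through.** The plan gives a direction but no figure, so there is none to reproduce. From Section 5.1 come Eqs. 1 to 3 and a = dose given. Assumed: L from 5 to 30%, and the pool sizes used below.

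**1. No loss.** From Eqs. 1 and 2, Fa − Fc = b(Fa − Fb)/(a + b) and Fc − Fb = a(Fa − Fb)/(a + b). Their ratio is b/a, so Eq. 3 returns b. A numerical check with a = 250, 605, 302.5 and 151.25 mg and b = 2,000, 10,000 and 40,000 mg returned b each time.

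**2. With loss.** Let P be the unlabelled choline in the pool at the Fc sample, at abundance Fb, and a(1−L) the label still there. Then Fa − Fc is proportional to P and Fc − Fb to a(1−L), so Eq. 3 gives a × P/[a(1−L)] = P/(1−L), whatever the dose or pool size.

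| Assumed L | Eq. 3 ÷ P | True fall of 1,000 mg in P, same L on both diets, reported as |
|---|---|---|
| 5% | 1.05 | 1,053 mg |
| 10% | 1.11 | 1,111 mg |
| 20% | 1.25 | 1,250 mg |
| 30% | 1.43 | 1,429 mg |

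Putting a(1−L) in place of a returns P exactly. Absorption of a fraction f gives the factor 1/f by the same algebra (1.11 at 90%), which is the direction the plan states for absorption.

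**3. Against the baseline pool b.**
- Loss before mixing: P = b, so the factor 1/(1−L) is exact.
- Well-mixed loss after a bolus: P = (1−L)b + U, where U is unlabelled choline that entered and is still present ("New Cho enters the pool from the diet and from" synthesis by PEMT). Eq. 3 gives b + U/(1−L). The part due to loss is UL/(1−L): zero if U = 0, and smaller than in the first case whenever U is below b.
- Example (all assumed): b = 5,000 mg, 550 mg/d unlabelled intake, three days. The ratio to b is 1.330 with no loss and 1.362 with a loss rate of 0.06 per day. There L = 1 − exp(−0.18) = 16.5%, so the factor against P is 1/0.835 = 1.20, while loss adds only 0.032 against b.

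**4. Changes between diets, for the pool at the Fc sample.**
- Equal L of 20%, true pools 100, 80 and 60 units: estimates 125, 100 and 75. Errors are 25, 20 and 15, so not constant. Changes read −25 and −50 against true −20 and −40. The ratios 0.80 and 0.60 are kept.
- Unequal L, true fall 10%: reported fall = 1 − 0.9 × (1 − L100)/(1 − Llow). With 15% and 10%: 1 − 0.9 × 0.85/0.90 = 15.0%. With 15% and 20%: 1 − 0.9 × 0.85/0.80 = 4.4%.
- Two people with the same pool and L of 5% and 15%: estimates differ by the factor 0.95/0.85 = 1.12.

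**The case against.** The best defence is that the plan knows label is lost, will measure it, and means to revise its assumptions. That stands: the gap is a missing rule, not a missed problem. A reader might infer that analysts would adjust in the stated wrong direction and compound the error. The documents do not support this. Section 5.1 speaks of revising how much label has left the pool, and a retained dose put into Eq. 3 corrects in the right direction whatever the prose says.

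Second, Aim 1 is judged by correlation. If L were the same in everyone on every diet, correlations, relative prediction error and the diet-by-genotype tests would not move, so it would be too strong to say that only ratios survive. This also stands, but equality is asserted and not shown. Equally, a reader might infer from the fall in plasma betaine on depletion (Section 1.1) that L differs by diet. That result concerns plasma concentration, not fractional urinary loss, and does not establish it.

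Third, under the five-day labelling text Eq. 3 can fall below the baseline pool. Assume b = 20,000 mg, the 25% diet and 10% of the pool lost over five days (k = −ln(0.9)/5 = 0.02107 per day). Label given is 0.22 × 137.5 × 5 = 151.25 mg. Label retained is 30.25 × 0.1/0.02107 = 143.56 mg. Unlabelled choline is 18,000 + 107.25 × 0.1/0.02107 = 18,509 mg. Eq. 3 gives about 19,500 mg, or 0.975 of baseline. This reflects a shrinking pool, which Section 5.1 discusses separately. Against the pool at the sample the result is still high: 19,500/18,509 = 1.054 = 1/(1 − 0.051), where 0.051 is the label fraction lost.

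**Conclusion.** The concern holds. For the pool present at the Fc sample, urinary loss makes Eq. 3 too large by 1/(1−L) under either labelling text, and the stated underestimate is wrong. This needs only a = dose given and unlabelled choline at abundance Fb. The claim that changes in pool size are unaffected is wrong for absolute changes at any L above zero. It is unsupported for ratios, correlations and tests unless L is equal across people and diets.

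Confidence is high for the sign and low for the size: the documents give no L, and every magnitude here is illustrative. Whether Aim 1 is harmed depends on variation in L, which the documents leave open.

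One further inference should be resisted: that equal L protects ratios of the baseline pool. It does not. Even at L = 0, Eq. 3 returns b + U after a well-mixed bolus, and unlabelled intake differs by diet.

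**What to change.** 1. **Correct the text of Section 5.1.** State that urinary loss leads to overestimation. Replace the statements that the error is constant and changes are unaffected with the actual condition: if fractional loss is equal across subjects and diets, ratios, correlations and tests for the pool at the Fc sample are protected, but absolute changes are not. This costs wording only.
2. **Put the loss into Eq. 3.** Name the blood sample that supplies Fc and define the target as the pool at that sample. Set a = dose given × (1−L), with L from labelled metabolites (at least the deuterated betaine and TMAO named in Section 5.1) in that subject's post-dose 24-hour urines for that period, up to that sample. Report uncorrected b beside it as a sensitivity analysis. Call the correction partial: label that has left the choline pool but is still in the body is not in urine. The costs are label assays in all subjects and periods if only a year-1 subset was budgeted, error from incomplete collections, and possible coupling of the response with betaine and trimethylamine oxide, which are also panel predictors.
3. **Separately, reconcile the labelling schedules.** Sections 3.1, 4.2 and 7 describe a day-12 dose of 250 mg; Sections 1.2 and 5.1 describe five days at 22% of dietary choline. Both a and the urine window depend on which applies, and the urines in Section 4.2 are timed from the day-12 dose. This is wording, unless the agreed schedule needs further collections.
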